APPENDIX V-B: PALBOCICLIB DOSING PREPARATION (LIQUID FORMULATION)

Drug doses should be adjusted based on the BSA calculated from height and weight measured within 7 days prior to the beginning of the cycle.

Patients receiving doses ≥ 75 mg/day may take either the capsule or liquid formulation. (See [Appendix V-A](#) for dosing nomogram for palbociclib capsule formulation).

Patients receiving < 75 mg/day of palbociclib must receive the liquid formulation.

Patients receiving the liquid formulation who experience dose-limiting toxicity should have their dose reduced by 30%, so that patients receive 70% of the original prescribed dose.

The concentration of palbociclib liquid formulation is 25 mg/mL.

Calculated doses < 18.75 mg should be prepared in oral syringes ≤ 1 mL with dosing volumes of palbociclib liquid formulation rounded to the nearest 0.1 mL (2.5 mg). Calculated doses > 18.75 mg should be prepared in 5 mL oral syringes with dosing volumes of palbociclib liquid formulation rounded to the nearest 0.2 mL (5 mg). It is recommended that oral dosing syringes should be only filled up to 75% of the maximum volume.

To calculate dosing volumes for each patient based on BSA, the following formula should be used:

$$\text{Dosing Volume (mL)} = \frac{\text{Prescribed Dose (mg/m}^2\text{)} \times \text{BSA (m}^2\text{)}}{25 \text{ (mg/mL)}}$$

Round dosing volumes according to the above rules.

Examples:

- Patient BSA 0.33 m^2 , Dose Level 1 (50 mg/m^2) \rightarrow Calculated Dose = 16.5 mg PO daily
 Calculated Volume (mL) = $(50 \text{ mg/m}^2 \times 0.33 \text{ m}^2) / (25 \text{ mg/mL}) = 0.66 \text{ mL}$
 Final Dosing Volume (mL) = 0.7 mL (rounded to nearest 0.1 mL for doses ≤ 18.75 mg)
 Final Dose to be administered = $0.7 \text{ mL} \times 25 \text{ mg/mL} = 17.5 \text{ mg}$
- Patient BSA 1.66 m^2 , Dose Level -1 (35 mg/m^2) \rightarrow Calculated Dose = 58.1 mg PO daily
 Calculated Volume (mL) = $(35 \text{ mg/m}^2 \times 1.66 \text{ m}^2) / (25 \text{ mg/mL}) = 2.324 \text{ mL}$
 Final Dosing Volume (mL) = 2.4 mL (rounded to the nearest 0.2 mL for dose > 18.75 mg)
 Final Dose to be administered = $2.4 \text{ mL} \times 25 \text{ mg/mL} = 60 \text{ mg}$

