5.2 Dosing Schema

5.2.1 Inter-Patient Dosing Schema

Dose Level	Palbociclib (mg/m ²)	Palbociclib max dose (mg/day)
-1	35	75
1*	50	100

If the MTD has been exceeded at the first dose level, then the subsequent cohort of patients will be treated at a dose of 35 mg/m² (Dose Level -1). If Dose Level -1 is not well tolerated, further de-escalation will not occur. The study will be closed to accrual.

See [Appendix V-A](#) and [Appendix V-B](#) for palbociclib capsule and liquid formulation dosing.

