6.1 Dose Modifications for Non-Hematological Toxicity Attributable to Palbociclib

- 6.1.1 If a patient experiences non-hematological dose-limiting toxicity as defined in [Section 5.4.1](#), palbociclib will be held until the toxicity is \leq Grade 1 or as otherwise indicated below (see [Section 6.2](#) for dose modifications for other backbone chemotherapy agents). When the toxicity resolves to meet eligibility parameters or baseline within 14 days of drug discontinuation, the patient may resume treatment at the next lower dose level. For patients enrolled at Dose Level -1, palbociclib should be discontinued but the backbone chemotherapy can be continued if this is not contributing to the toxicity. Doses reduced for toxicity will not be re-escalated, even if there is minimal or no toxicity with the reduced dose. Missed doses will not be made up.
- 6.1.2 If toxicity does not resolve to meet eligibility or baseline parameters within 14 days of drug discontinuation, the patient must be removed from protocol therapy.
- 6.1.3 If a dose-limiting toxicity recurs in a patient who has resumed treatment at the reduced dose level, the patient must be removed from protocol therapy.

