10.0 CRITERIA FOR REMOVAL FROM PROTOCOL THERAPY AND OFF STUDY CRITERIA

10.1 Criteria for Removal from Protocol Therapy

- a) Clinical (including physical examination or serum tumor markers) or radiographic evidence of progressive disease (See [Section 12](#)).
- b) Adverse Events requiring removal from protocol therapy (See [Section 6](#)).
- c) Refusal of protocol therapy by patient/parent/guardian
- d) Non-compliance that in the opinion of the investigator does not allow for ongoing participation.
- e) Completion of planned therapy.
- f) Physician determines it is not in the patient's best interest.
- g) Repeated eligibility laboratory studies (bilirubin, ALT (SGPT) or serum creatinine) are outside the parameters required for eligibility prior to the start of systemic chemotherapy (See [Section 8.1](#)).
- h) Study is terminated by Sponsor.
- i) Pregnancy

Patients who are removed from protocol therapy during Cycle 1 should continue to have the required observations in [Section 8.1](#) until the originally planned end of the cycle or until all adverse events have resolved per [Section 13.4.4](#), whichever happens LATER. The only exception is with documentation of the patient's withdrawal of consent. Patients who are removed from protocol therapy in subsequent cycles should have the necessary observations to ensure adequate clinical care.

Patients who are off protocol therapy are to be followed until they meet the criteria for Off Study (see below). Ongoing adverse events, or adverse events that emerge after the patient is removed from protocol therapy, but within 30 days of the last dose of investigational agent, must be followed and reported via RAVE and SAE Report submitted via RAVE (if applicable). Follow-up data will be required unless consent is withdrawn.

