APPENDIX V-A: Palbociclib Capsule Dosing Nomogram

Drug doses should be adjusted based on the BSA calculated from height and weight measured within 7 days prior to the beginning of each cycle.

Palbociclib is available as 75 mg and 100 mg capsules. Patients receiving doses ≥ 75 mg/day may take either the capsule or liquid formulation. Patients receiving < 75 mg/day of palbociclib must receive the liquid formulation (See [Appendix V-B](#) for dosing preparation of palbociclib liquid formulation.)

**Palbociclib Dose Assignment: 50 mg/m²
(Dose Level 1)**

BSA (m ²)	Total Daily Dose (mg/day)	Dose Reduction for Toxicity (mg/day)
< 1.37	Use liquid formulation (see Appendix V-B)	Reduce dose by 30%. Use liquid formulation (see Appendix V-B)
1.37-1.74	75	Reduce dose by 30%. Use liquid formulation (see Appendix V-B)
≥ 1.75	100	75

**Palbociclib Dose Assignment: 35 mg/m²
(Dose Level -1)**

BSA (m ²)	Total Daily Dose (mg/day)	Dose Reduction for Toxicity (mg/day)
<1.95	Use liquid formulation (see Appendix V-B)	off protocol therapy
≥ 1.95	75	off protocol therapy

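### After a DLT, Section 6.1.1 and Appendices V-A and V-B give conflicting palbociclib instructions: three different actions at Dose Level -1, and 75 mg against 60-70 mg at Dose Level 1 for BSA 1.75-1.94

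*Combined protocol and SAP*

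**What the plan says.** Section 6.1.1 governs non-hematological DLT. Palbociclib is held, and if the toxicity resolves in time "the patient may resume treatment at the next lower dose level". Section 5.2.1 has only two levels, so for a Dose Level 1 patient (50 mg/m²) the next lower one is Dose Level -1 (35 mg/m², at most 75 mg/day). For patients already enrolled at Dose Level -1, "palbociclib should be discontinued but the backbone chemotherapy can be continued if this is not contributing to the toxicity".

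Appendix V-A (capsule nomogram) has its own dose-reduction column. At Dose Level 1, BSA 1.75 and above goes from 100 mg to 75 mg, and smaller patients are cut by 30% using the liquid. At Dose Level -1, both BSA rows read "off protocol therapy". That table also puts everyone with BSA below 1.95 on the liquid and refers them to Appendix V-B.

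Appendix V-B (liquid) states: "Patients receiving the liquid formulation who experience dose-limiting toxicity should have their dose reduced by 30" percent. It makes no exception for Dose Level -1, and the second of its two worked examples is a Dose Level -1 patient.

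Section 5.1 directs sites to V-A and V-B for dosing. Section 10.1(b), "Adverse Events requiring removal from protocol therapy", refers to Section 6. No text states which prevails when they differ.

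**The concern.** These instructions apply to a patient who has just had a DLT attributed at least possibly to palbociclib.

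At Dose Level -1, a site that follows V-B keeps giving a drug that Section 6.1.1 stops, at a dose that Section 5.2.1 does not contain. A site that follows V-A ends protocol re-induction that Section 6.1.1 would allow to go on. Stopping palbociclib is not the same as leaving protocol therapy: the backbone is part of the treatment program, and Sections 6.1.2 and 6.1.3 use removal from protocol therapy as a separate, stronger step.

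At Dose Level 1, a capsule patient with BSA 1.75-1.94 restarts above the level that Section 6.1.1 names, and under Section 6.1.3 a recurrent DLT means removal.

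**Working it through.** **Inputs.** Dose levels of 50 and 35 mg/m² (Section 5.2.1). Liquid at 25 mg/mL, with doses above 18.75 mg rounded to the nearest 0.2 mL, i.e. 5 mg (Appendix V-B). Capsule rows and reduction column from Appendix V-A.

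**Formula (V-B).** Volume = prescribed dose × BSA / 25, then rounded.

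**Reproducing V-B's own examples.**
- BSA 1.66 at 35 mg/m²: 58.1 mg / 25 = 2.324 mL, rounded to 2.4 mL = 60 mg, as printed.
- BSA 0.33 at 50 mg/m²: 16.5 mg / 25 = 0.66 mL, rounded to 0.7 mL (0.1 mL steps for small doses) = 17.5 mg, as printed.

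**Dose Level -1 after a DLT, BSA 1.66, on 60 mg/day.**

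| Source | Action |
|---|---|
| Section 6.1.1 | 0 mg; backbone may continue |
| Appendix V-A | Off protocol therapy |
| Appendix V-B | 0.7 × 58.1 = 40.67 mg = 1.627 mL, rounded to 1.6 mL = 40 mg/day |

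Taking 70% of the rounded 60 mg gives 42 mg = 1.68 mL, which also rounds to 40 mg. The nominal V-B dose is 0.7 × 35 = 24.5 mg/m²; the dose given is 40 / 1.66 = 24.1 mg/m².

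Liquid patients face all three actions: everyone below BSA 1.95, and anyone at or above it who takes the liquid. Capsule patients at Dose Level -1 face the first two.

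**Dose Level 1 after a DLT, capsules, BSA 1.75-1.94.** V-A goes from 100 to 75 mg, a 25% cut. The comparison is the V-B liquid dose at 35 mg/m², which is what V-A's Dose Level -1 table requires at these sizes.

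| BSA | 35 × BSA (mg) | Liquid dose given | V-A reduced dose | Excess | V-A dose per m² |
|---|---|---|---|---|---|
| 1.75 | 61.25 | 2.4 mL = 60 mg | 75 mg | 75/60 = +25.0% | 42.9 |
| 1.80 | 63.0 | 2.6 mL = 65 mg | 75 mg | 75/65 = +15.4% | 41.7 |
| 1.94 | 67.9 | 2.8 mL = 70 mg | 75 mg | 75/70 = +7.1% | 38.7 |

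Over the 20 BSA values from 1.75 to 1.94 in steps of 0.01, the liquid dose is 60 mg at 4 (1.75-1.78), 65 mg at 14 (1.79-1.92) and 70 mg at 2 (1.93-1.94). Against the nominal 35 mg/m², V-A delivers 42.86/35 = +22.4% at BSA 1.75 and 38.66/35 = +10.5% at BSA 1.94. The mean over the band is 40.7 mg/m², or +16.3%. The step between the two levels is 30%.

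**Where there is no conflict.** At BSA 1.95 and above, both V-A tables give 75 mg. For Dose Level 1 liquid patients, V-B's cut is 0.7 × 50 = 35 mg/m², which is Dose Level -1.

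**The case against.** **Sites are pointed to Section 6 after a DLT.** The Therapy Delivery Maps say so, and so does Section 10.1(b). This supports making Section 6.1.1 the standard, but it is not a precedence rule, and V-A and V-B carry explicit toxicity instructions of their own.

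**There are safeguards.** A suspected DLT goes to the Study Chair within 24 hours (Section 5.3), dose modifications must be notified (Section 6.0), and leadership reviews data weekly (Section 14.2.2). These make an unnoticed error less likely. They do not say which instruction is right.

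**V-B's sentence may be meant only for Dose Level 1.** Since 70% of 50 is exactly 35, that is a plausible intent. The text does not say it, V-B's second example is at Dose Level -1, and V-A's row for these patients both says off protocol therapy and sends the reader to V-B. Even on the narrow reading, V-A and Section 6.1.1 still disagree on the backbone.

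**75 mg is the capsule nearest to 70 mg.** Counted from 100 mg, the gap is only 5 mg. But V-A already moves reduced patients with BSA 1.37-1.74 from capsule to liquid, and requires liquid for Dose Level -1 patients in the 1.75-1.94 band, so rounding to a capsule is not its consistent rule.

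**Day 32 assessments continue after removal.** This stands: Section 10.1 keeps the required observations going to at least the planned end of the cycle. What differs is the treatment behind the response, not whether it is assessed.

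**It will be rare.** This also stands. Dose Level -1 opens only if Dose Level 1 exceeds the MTD. Hematological DLT is judged at Day 42, after palbociclib ends on Day 21, and some non-hematological DLTs will be established too late for any dosing to resume.

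**Conclusion.** The concern holds. At Dose Level -1 the three texts give liquid patients three incompatible actions, and capsule patients two. At Dose Level 1, for BSA 1.75-1.94, V-A's reduced dose is 5-15 mg/day above the dose for Dose Level -1. The Dose Level -1 conflict is the weightier one, because it decides whether the suspected drug and the protocol backbone continue.

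This rests on taking the next lower level as 35 mg/m², on V-B's rounding rule, and, for the third action, on reading V-B's sentence as written.

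The effect is limited. The DLT is already counted, so the MTD decision does not move. Only patients with a non-hematological DLT during the 21 dosing days are exposed, in cohorts of 6 (12 if expanded) plus up to 6 in the expansion. It should be corrected because literal compliance with either appendix can depart from Section 6.1.1 at the point where the patient is most at risk.

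**What to change.** Align both appendices to Section 6.1.1:

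- **V-A, Dose Level 1:** split the row for BSA 1.75 and above. For 1.75-1.94: 100 mg, reduced to liquid at 35 mg/m² per V-B. For 1.95 and above: 100 mg, reduced to a 75 mg capsule.
- **V-A, Dose Level -1:** in both rows, replace the reduction entry with an instruction to discontinue palbociclib and handle the backbone per Section 6.1.1.
- **V-B:** limit the 30% reduction to Dose Level 1, and add that at Dose Level -1 palbociclib is discontinued (Section 6.1.1).

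The cost is one row split, two cells and one sentence. Capsule patients with BSA 1.75-1.94 who are reduced would change to the liquid already supplied, as V-A already requires of reduced patients below BSA 1.75. Design and sample size are untouched.

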APPENDIX VI: THERAPY DELIVERY MAP (TDM) (PATIENTS WITH ALL)

Therapy Delivery Map – Cycle 1 This Therapy Delivery Map (TDM) relates to Cycle 1. Cycle 1 lasts 32 days. This TDM can be used for all dose levels of palbociclib. Please record the dose level below. This TDM is intended to serve as a tool to assist in scheduling the required observations for the study; the schedule indicated in the chart below should be considered an example. The actual schedule must comply with the timing of required observations per Section 8 of the protocol. This form is to be completed and uploaded into RAVE at the end of Cycle 1.
	
_____ Accession #
 
_____ Patient COG ID number
 
_____ Institution

--	--

DRUG	ROUTE	DOSAGE	DAYS	IMPORTANT NOTES
Palbociclib IND #141416	PO (or NG- Tube)	Dose Level -1: 35 mg/m ² Dose Level 1: 50 mg/m ²	Once daily on Days 1-21	Dose Level -1: MAX dose 75 mg Dose Level 1: MAX dose 100 mg
Intrathecal Cytarabine (IT ARAC): All patients on Day 1 (before CNS status is known)	IT	Age (yrs) Dose 1-1.99 30 mg 2-2.99 50 mg ≥3 70 mg	1@	Note age-based dosing @Patients with known CNS3 disease at the time of study enrollment may receive triple intrathecal chemotherapy on Day 1 as a substitute for intrathecal cytarabine, at the discretion of the treating investigator. Patients are NOT to receive both intrathecal triples and intrathecal cytarabine on Day 1, regardless of CNS status.
Intrathecal Methotrexate (IT MTX): CNS1 and 2	IT	Age (yrs) Dose 1-1.99 8 mg 2-2.99 10 mg 3-8.99 12 mg ≥9 15 mg	18,32	Note age-based dosing
Intrathecal Triple Therapy (ITT): Methotrexate (MTX)/ Hydrocortisone (HC)/Cytarabine (ARAC) if CNS3	IT	Age (yrs) Dose 1-1.99 MTX:8mg, HC: 8mg, ARAC: 16mg 2-2.99 MTX: 10mg HC: 10 mg ARAC: 20 mg 3-8.99 MTX: 12 mg HC: 12 mg ARAC: 24 mg ≥9 MTX: 15 mg HC: 15 mg ARAC: 30 mg	1@, 4, 11, 18, 25	Note age-based dosing @Patients with known CNS3 disease at the time of study enrollment may receive triple intrathecal chemotherapy on Day 1 as a substitute for intrathecal cytarabine, at the discretion of the treating investigator. Patients are NOT to receive both intrathecal triples and intrathecal cytarabine on Day 1, regardless of CNS status.
DOXOrubicin (DOXO)	slow IV push or infusion over 1- 15 min	60 mg/m ² /dose	4	Administer through the tubing of a rapidly infusing D5W or 0.9% NaCL solution
PredniSO(LO)NE (PRED)*	PO	40 mg/m ² /day divided BID or TID	4-31	
VinCRIStine (VCR)	IV push over 1 min ⁺	1.5 mg/m ² /dose (MAX dose 2 mg)	4, 11, 18, 25	⁺ + Or infusion via minibag as per institutional policy Maximum dose: 2 mg

Pegaspargase (PEG-ASP)	IV over 1-2 hours	2500 International units/m ² /dose	5, 18	Administer IV infusion through the tubing of a rapidly infusing D5W or 0.9% NaCL solution. See section 5.1 for special precautions with pegaspargase administration.
-------------------------------	----------------------	---	-------	---

* IV methylprednisolone may be given at 80 % of the oral predniSONE or predniSOLONE dose.

NOTE: All patients should receive trimethoprim/sulfamethoxazole (TMP/SMX) at a dose of TMP 2.5 mg/kg/dose (maximum dose 160 mg/dose) by mouth twice daily on 2 or 3 sequential days per week.

Assigned Dose Level _____ Ht _____ cm Wt _____ kg BSA _____ m²

Date Due	Date Given	Day	Palbociclib _____ mg	IT ARAC _____ mg	IT MTX (CNS 1 and 2) _____ mg	Intrathecal Triple Therapy (CNS3): MTX/ HC/ ARAC mg/ mg/ mg	DOXO _____ mg	PRED _____ mg BID or TID	VCR _____ mg	PEG-ASP _____ IU	Studies to be obtained
		1	_____ mg	_____ mg		_____ mg					
		2	_____ mg								i
		3	_____ mg								
		4	_____ mg			MTX/ HC/ ARAC mg/ mg/ mg	_____ mg	__ mg __ mg __ mg	_____ mg		a, b, f, h, j, p, q,n
		5	_____ mg							IU	
		6	_____ mg								
		7	_____ mg								
		8	_____ mg								f
		9	_____ mg								
		10	_____ mg								
		11	_____ mg			MTX/ HC/ ARAC mg/ mg/ mg			_____ mg		a, b, f, h, i, j,n
		12	_____ mg								i
		13	_____ mg								
		14	_____ mg								
		15	_____ mg								f
		16	_____ mg								
		17	_____ mg								
		18	_____ mg		_____ mg	MTX/ HC/ ARAC mg/ mg/ mg			_____ mg	_____ IU	a, b, f, h, j,n
		19	_____ mg								
		20	_____ mg								
		21	_____ mg								
		22									f
		23									
		24									
		25				MTX/ HC/ ARAC mg/ mg/ mg			_____ mg		a, b, f, h, j,n
		26									
		27									
		28									

		29									f
		30									
		31									
		32 [^]			_____ mg						a, b, c, d, f, h, j, l, m, o, n

[^] Abnormal laboratory tests must be re-checked by Day 42 since some toxicities require resolutions to \leq Grade 2 or baseline by Day 42 (see DLT criteria).

See [Section 6.0](#) for Dose Modifications for Adverse Events and [Section 7.0](#) and the COG Member website for Supportive Care Guidelines

Required Observations in Cycle 1

All baseline studies must be performed prior to starting protocol therapy unless otherwise indicated below. For information related to prestudy observations please refer to [Section 8.0](#)

- a. History
- b. Physical exam with vital signs
- c. Height, weight, BSA
- d. Performance status
- e. Pregnancy test: Women of childbearing potential require a negative pregnancy test prior to starting treatment; sexually active patients must use an acceptable method of birth control. Abstinence is an acceptable methods of birth control. All women of childbearing potential must have a pregnancy test done every cycle prior to initiation of a new cycle.
- f. CBC, differential, platelets: Twice weekly during Cycle 1. If patients have Grade 4 neutropenia or thrombocytopenia, CBCs should be checked at least every other day until recovery to Grade 3 or until the criteria for dose limiting toxicity are met.
- g. Urinalysis
- h. Electrolytes including Ca⁺⁺
- i. Pharmacokinetics (required): See [Section 8.2](#) for details.
- j. Creatinine, ALT, bilirubin
- k. Albumin
- l. ECHO or gated radionuclide study
- m. 12-lead EKG
- n. Patient Diary
- o. Bone Marrow Aspirate for morphology and MRD. Must be performed on Day 32 ± 2 days.
- p. Absolute Blast Count; Absolute blast count should be performed on Day 4 prior to administration of chemotherapy.
- q. Correlative Biology Studies See Section 8.3 for details.

This listing only includes evaluations necessary to answer the primary and secondary aims. OBTAIN OTHER STUDIES AS REQUIRED FOR GOOD CLINICAL CARE.

Comments

(Include any held doses, or dose modifications)

APPENDIX VII: THERAPY DELIVERY MAP (TDM) (PATIENTS WITH LL)

Therapy Delivery Map – Cycle 1 This Therapy Delivery Map (TDM) relates to Cycle 1. Cycle 1 lasts 32 days. This TDM can be used for all dose levels of palbociclib. Please record the dose level below. This TDM is intended to serve as a tool to assist in scheduling the required observations for the study; the schedule indicated in the chart below should be considered an example. The actual schedule must comply with the timing of required observations per Section 8 of the protocol. This form is to be completed and uploaded into RAVE at the end of Cycle 1.
	
_____ Accession #
 
_____ Patient COG ID number
 
_____ Institution

--	--

DRUG	ROUTE	DOSAGE	DAYS	IMPORTANT NOTES
Palbociclib IND #141416	PO (or NG-tube)	Dose Level -1: 35 mg/m ² Dose Level 1: 50 mg/m ²	Once daily on Days 1-21	Dose Level -1: MAX dose 75 mg Dose Level 1: MAX dose 100 mg
Intrathecal Cytarabine (IT ARAC): All patients on Day 1 (before CNS status is known)	IT	Age (yrs) Dose 1-1.99 30 mg 2-2.99 50 mg ≥3 70 mg	1@	Note age-based dosing @Patients with known CNS3 disease at the time of study enrollment may receive triple intrathecal chemotherapy on Day 1 as a substitute for intrathecal cytarabine, at the discretion of the treating investigator. Patients are NOT to receive both intrathecal triples and intrathecal cytarabine on Day 1, regardless of CNS status.
Intrathecal Methotrexate (IT MTX): CNS1 and 2	IT	Age (yrs) Dose 1-1.99 8 mg 2-2.99 10 mg 3-8.99 12 mg ≥9 15 mg	18,32	Note age-based dosing
Intrathecal Triple Therapy (ITT): Methotrexate (MTX)/ Hydrocortisone (HC)/Cytarabine (ARAC) if CNS3	IT	Age (yrs) Dose 1-1.99 MTX:8mg, HC: 8mg, ARAC: 16mg 2-2.99 MTX: 10mg HC: 10 mg ARAC: 20 mg 3-8.99 MTX: 12 mg HC: 12 mg ARAC: 24 mg ≥9 MTX: 15 mg HC: 15 mg ARAC: 30 mg	1@, 4, 11, 18, 25	Note age-based dosing @Patients with known CNS3 disease at the time of study enrollment may receive triple intrathecal chemotherapy on Day 1 as a substitute for intrathecal cytarabine, at the discretion of the treating investigator. Patients are NOT to receive both intrathecal triples and intrathecal cytarabine on Day 1, regardless of CNS status.
DOXOrubicin (DOXO)	slow IV push or infusion over 1-15 min	60 mg/m ² /dose	4	Administer through the tubing of a rapidly infusing D5W or 0.9% NaCL solution
PredniSO(LO)NE (PRED)*	PO	40 mg/m ² /day divided BID or TID	4-31	
VinCRIStine (VCR)	IV push over 1 min ⁺	1.5 mg/m ² /dose (MAX dose 2 mg)	4, 11, 18, 25	⁺ + Or infusion via minibag as per institutional policy Maximum dose: 2 mg

Pegaspargase (PEG-ASP)	IV over 1-2 hours	2500 International units/m ² /dose	5, 18	Administer IV infusion through the tubing of a rapidly infusing D5W or 0.9% NaCL solution. See section 5.1 for special precautions with pegaspargase administration.
-------------------------------	----------------------	---	-------	--

* IV methylprednisolone may be given at 80 % of the oral predniSONE or predniSOLONE dose.

NOTE: All patients should receive trimethoprim/sulfamethoxazole (TMP/SMX) at a dose of TMP 2.5 mg/kg/dose (maximum dose 160 mg/dose) by mouth twice daily on 2 or 3 sequential days week. **Assigned Dose Level** _____ **Ht** _____ **cm** **Wt** _____ **kg** **BSA** _____ **m²**

Date Due	Date Given	Day	Palbociclib _____ mg	IT ARAC _____ mg	IT MTX (CNS 1 and 2) _____ mg	Intrathecal Triple Therapy (CNS3): MTX/ HC/ ARAC mg/ mg/ mg	DOXO _____ mg	PRED _____ mg BID or TID	VCR _____ mg	PEG-ASP _____ IU	Studies to be obtained
		1	_____ mg	_____ mg							
		2	_____ mg								i
		3	_____ mg								
		4	_____ mg			MTX/ HC/ ARAC mg/ mg/ mg	_____ mg	__ mg __ mg __ mg	_____ mg		a, b, f, h, j, n
		5	_____ mg							_____ IU	
		6	_____ mg								
		7	_____ mg								
		8	_____ mg								f
		9	_____ mg								
		10	_____ mg								
		11	_____ mg			MTX/ HC/ ARAC mg/ mg/ mg			_____ mg		a, b, f, h, i, j, n
		12	_____ mg								i
		13	_____ mg								
		14	_____ mg								
		15	_____ mg								f
		16	_____ mg								
		17	_____ mg								
		18	_____ mg		_____ mg	MTX/ HC/ ARAC mg/ mg/ mg			_____ mg	_____ IU	a, b, f, h, j, n
		19	_____ mg								
		20	_____ mg								
		21	_____ mg								
		22									f
		23									
		24									
		25				MTX/ HC/ ARAC mg/ mg/ mg			_____ mg		a, b, f, h, j, n
		26									
		27									
		28									
		29									f

		30									
		31									
		32^			_____ mg						a, b, c, d, f, h, j, l, m, o, p, q, r, s,n

^ Abnormal laboratory tests must be re-checked by Day 42 since some toxicities require resolutions to ≤ Grade 2 or baseline by Day 42 (see DLT criteria).

See [Section 6.0](#) for Dose Modifications for Adverse Events and [Section 7.0](#) and the COG Member website for Supportive Care Guidelines.

Required Observations in Cycle 1

All baseline studies must be performed prior to starting protocol therapy unless otherwise indicated below. For information related to prestudy observations please refer to [Section 8.0](#).

- a. History
- b. Physical exam with vital signs
- c. Height, weight, BSA
- d. Performance status
- e. Pregnancy test: Women of childbearing potential require a negative pregnancy test prior to starting treatment; sexually active patients must use an acceptable method of birth control. Abstinence is an acceptable methods of birth control.
- f. CBC, differential, platelets: Twice weekly during Cycle 1. If patients have Grade 4 neutropenia or thrombocytopenia, CBCs should be checked at least every other day until recovery to Grade 3.
- g. Urinalysis
- h. Electrolytes including Ca⁺⁺
- i. Pharmacokinetics (required): See [Section 8.2](#) for details.
- j. Creatinine, ALT, bilirubin
- k. Albumin
- l. ECHO or gated radionuclide study
- m. 12-lead EKG
- n. Patient Diary
- o. Chest and neck CT. Obtain chest CT for all LL patients at baseline and on Day 32. The baseline chest CT may be delayed until the patient is stable. A PET-CT can be used instead of a CT.
- p. Abdomen/Pelvis CT or MRI. If scans are negative at baseline, not further imaging is needed on Day 32. A PET-CT can be used instead of a CT.
- q. PET scan (recommended)
- r. Bone scan. Bone scan only if patient has symptoms; perform at Day 32 only if patient has disease at baseline. May substitute a PET scan for a bone scan, however, a bone scan is preferred for bone symptoms.
- s. Bilateral bone marrow aspirates and biopsies for morphology. LL should have bone marrow aspirates and biopsies on Day 32 ± 2 days if ≥ 5% marrow involvement was present at diagnosis

This listing only includes evaluations necessary to answer the primary and secondary aims. OBTAIN OTHER STUDIES AS REQUIRED FOR GOOD CLINICAL CARE.

Comments

(Include any held doses, or dose modifications)

